4. STATISTICAL CONSIDERATIONS

Data analysis will be performed according to the Sponsor's representative Standard Operating Procedures (SOPs).

The general analytical approach for all endpoints will be descriptive in nature. All summaries will present the data by dose group as well as by all participants combined.

Unless otherwise stated, the following statistical approaches will be taken:

Continuous variables:	Descriptive statistics will include the number of non-missing values, mean, standard deviation (SD), CV%, median, interquartile range, minimum, and maximum. The minimum and maximum values will be presented to the same number of decimal places as recorded in the raw data; mean and median will be presented to 1 decimal place more than raw data; and SD will be presented to two more decimal places than the raw data. The number of decimals for lab parameters may be reduced if the full presentation of the data includes more than 4 significant figures. In general, the mean and median will be reported with one decimal place more than the data, and the standard deviation will be reported with two decimal places more than the data.
Categorical variables:	Descriptive statistics will include frequency counts and percentages per category. Percentages will be rounded to one decimal place, with the denominator being the number of patients in the relevant population.
Imputation:	No imputation will be performed for missing data.
Confidence intervals (CIs):	CIs will be two-sided and will use 95% confidence levels. Any analyses requiring significance testing will use a two-sided test at the 5% significance level.
Unscheduled Visits	Unscheduled visits that do not have laboratory data on the same visit date will be excluded from summary tables.
Early termination visit	Assessments conducted at Early Termination will be excluded from visit-based summary tables.

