10.4 Pharmacodynamics

10.4.1 Malaria 18S qPCR

Blood will be collected to quantify total malaria parasitemia by quantitative polymerase chain reaction targeting the gene encoding *P. falciparum* 18S rRNA (malaria 18S qPCR; reported as parasites/500uL packed RBCs). Malaria 18S qPCR data will be used to calculate the total parasite counts. Blood for malaria 18S qPCR will be collected on Day 0 prior to inoculation with the malaria challenge agent, then once daily on Days 4, 5, 6 and 7. On Day 8, blood will be collected pre-Pyronaridine tetraphosphate administration, then at the following hours post-Pyronaridine tetraphosphate administration while confined in the clinical unit: 4, 8, 12, 16, 20, 24, 30, 36, 42, 48, 60, 72, 84 and 96 hours. As outpatients, participants will have blood collected at least three times per week until antimalarial rescue treatment.

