11.1.2 Parasite clearance kinetics

The Parasite Reduction Ratio (PRR) and corresponding parasite clearance half-life (PCt_{1/2}) of asexual parasites is derived from the clearance rate of parasitaemia after administration of pyronaridine treatment. The analysis of PD response to investigational antimalarial therapy consists of:

- calculating the optimal parasite clearance rate (slope coefficient from the log-linear decay regression of qPCR data) for each individual, then,
- estimating dose specific parasite clearance rate and 95% confidence interval (CI) by calculating the weighted average slope estimate and corresponding standard error (SE) using an inverse-variance method.

The data used for all model selection and fitting calculations is comprised of the log₁₀ transformed geometric mean of parasitaemia per timepoint per participant up to the first timepoint all parasitaemia replicates are ND. If during initial parasite clearance there are no samples ND for a participant, the last timepoint included in the analyses will be three timepoints after the minimum observed parasitemia value. All subsequent timepoints are set to 'missing' regardless of whether parasitaemia values increased afterwards due to potential recrudescence. Sensitivity analyses may be performed using other thresholds to determine parasite clearance, for example, but not limited to, the lower limit of quantification (LOQ) (i.e. the lower limit of the reportable range) of 32 parasites/mL or limit of detection of 111 parasites/mL [1], to assess robustness of PRR estimates.

The PRR per 48 hours, PRR₄₈, for asexual parasite will be estimated using the slope of the optimal fit of the log-linear relationship of the parasitaemia decay over time from pyronaridine administration for each individual, as detailed in CTM QIMR SOP 41 and Marquart et al. [8].

Table 1: Symbols and definitions of terms used in parasite clearance analysis (Part 1)

Symbol	Definition
PRR _{48,i}	Individual specific Parasite Reduction Ratio per 48 h
PRR _{48,D}	Dose specific Parasite Reduction Ratio per 48 h
$\beta_{1,i}$	Slope coefficient of log10 parasitaemia vs. time profile for individual i
SE $_{\beta_{1,i}}$	SE corresponding to $\beta_{1,i}$ for individual i
$\bar{\beta}_{1,D}$	Dose specific average slope estimate
SE($\bar{\beta}_{1,D}$)	Weighted SE of dose specific average slope estimate
PCt _{1/2}	Parasite clearance half-life

Regression Modelling to Determine Optimal Fit

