A regression modelling approach to remove potential lag and/or tail phases of the parasitaemia decay profile will be used to determine the optimal log-linear decay regression. The algorithm considers removing parasitaemia data points in an iterative process from both ends of the parasitaemia curve, i.e. a combination of right censoring (removing values from the tail phase) and left censoring (removing values from the lag phase), and uses model selection techniques to find the optimal log-linear regression.

The algorithm to obtain the log-linear decay for each participant is based on the log-linear regression detailed in Equation (1), where Time is the number of hours since administration of antimalarial treatment ($Time = 1, \dots, m$), and β_0 and β_1 are the intercept and slope estimates, respectively.

$$\log_{10} Parasitemia = \beta_0 + \beta_1 Time \quad (1)$$

Based on the parasitaemia data for each participant, the iterative algorithm to determine the optimal log-linear decay for each participant is summarised in Table 2. The iterative algorithm is continued until a minimum of four observations are available.

The optimal log-linear regression model for a participant is deemed an appropriate fit if the overall model p-value < 0.001 .

Table 1: Iteration process to determine the optimal log-linear decay curve.

Step 1: For each participant, fit the full model - fit a linear regression (as defined by Equation 1) to all m parasitaemia values of participant i

Step 2: Fit two models:

- (a) Fit linear regression model to $m - 1$ parasitaemia values, removing the first observation.
- (b) Fit linear regression model to $m - 1$ parasitaemia values, removing the last observation.

Step 3: Determine the best model of Step 2(a) and Step 2(b), defined as the model corresponding to the minimum overall model p-value.

Step 4: Of the best model defined in Step 3, repeat Step 2 and Step 3 in an iterative process until a minimum of four observations.

Step 5: Of the $m - 3$ best models selected per iteration (including the full model (Step 1)), the optimal model was defined by the minimum overall model p-value.

Estimating Participant Specific PRR

The slope and corresponding SE estimate of the optimal linear regression model is used to calculate the participant specific PRR_{48} estimate and corresponding 95% confidence interval (95% CI), as shown in Equation (2) and (3), respectively.

$$PRR_{48,i} = 10^{-48 \times \beta_{1,i}} \quad (2)$$

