$$95\% \text{ CI: } 10^{-48(\beta_{1,i} \pm 1.96 \times SE(\beta_{1,i}))} \quad (3)$$

where $\beta_{1,i}$ and $SE_{\beta(1,i)}$ are the slope and corresponding standard error of the slope parameter of the optimal linear regression model, respectively.

Estimating Dose Specific PRR (PRR_{48,D})

Of the s participants with appropriate overall fit ($p < 0.001$), the average PRR_{48} and corresponding 95% CI for each cohort is estimated by using the inverse variance method to calculate the weighted average linear regression slope ($\bar{\beta}_1$) and corresponding SE. The weighted average slope for s participants in the dose with appropriate overall fit is given by Equation (4):

$$\bar{\beta}_1 = \frac{\sum_{i=1}^s (w_i \times \beta_{1,i})}{\sum_{i=1}^s w_i}, \quad i = 1, \dots, s \quad (4)$$

where the weight is the inverse of the squared standard error, $w_l = \frac{1}{SE(\beta_{1,l})^2}$. The standard error of $\bar{\beta}_1$ is estimated as, $SE(\bar{\beta}_1) = \sqrt{\frac{1}{\sum_{l=1}^s w_l}}$.

Therefore the dose specific PRR (PRR_{48,D}) and corresponding 95% confidence interval is estimated as shown in Equation (5) and (6), respectively:

$$PRR_{48,D} = 10^{-48 \times \bar{\beta}_1} \quad (5)$$

$$95\% CI: 10^{-48 \times (\bar{\beta}_1 \pm 1.96 \times SE(\bar{\beta}_1))} \quad (6)$$

Parasite Clearance Half Life

The parasite clearance half-life (PCt_{1/2}) will be derived from the optimal decay rate. The relationship between PRR₄₈ and parasite clearance half-life (PCt_{1/2}) is a simple transformation of the PRR₄₈ as shown in Equation (7):

$$PCt_{1/2} = \log_{10}(2) \times \left(\frac{48 \text{ hours}}{\log_{10}(PRR_{48,l})} \right) = \frac{\log_{10}(2)}{-\beta_{1,l}} \quad (7)$$

where PRR_{48,i} is the parasitaemia ratio estimated over a 48-hour interval that is subsequently transformed into a per hour clearance rate.

Comparison of Dose Specific PRR₄₈

To determine whether there are differences between dose specific PRRs, an omnibus test for between group differences is used. The test is used to assess whether there are differences in the weighted mean slope of the J doses, using the test statistic shown in Equation (8),

$$Q_B = \sum_{j=1}^J w_{j.} (\bar{\beta}_{j.} - \bar{\beta}_{..})^2 \sim \chi_{J-1}^2 \quad j = 1, \dots, J \quad (8)$$

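### The participant-specific 95% CI for PRR48 (SAP Equation 3) uses 1.96 where the standard error has only n−2 degrees of freedom, so it falls short of 95% even before window selection

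*SAP*

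**What the plan says.** SAP section 4 sets the general rule: "CIs will be two-sided and will use 95% confidence levels".

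SAP 11.1.2 then fits a straight line, with intercept and slope, to each participant's log10 parasitaemia against time (Equation 1). The data are the log10-transformed "geometric mean of parasitaemia per timepoint per participant up to the first timepoint all parasitaemia replicates are ND", so the triplicates are collapsed and each timepoint supplies one value.

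Points are trimmed from either end, and the window with the smallest overall p-value is kept. On how far trimming may go, the SAP says: "The iterative algorithm is continued until a minimum of four observations are available". A fit is called appropriate if its p-value is below 0.001.

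Equation (3) forms the participant's 95% CI as slope ± 1.96 × SE, carried to the PRR48 scale. It defines its inputs as the "slope and corresponding standard error of the slope parameter of the optimal linear regression model, respectively". The section contains no t quantile, no small-sample correction and no allowance for window selection. It does refer to an SOP and a published method, which were not available for this review.

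**The concern.** The value 1.96 is the two-sided 95% normal quantile. It gives 95% coverage only when the standard error is known. Here the SE comes from the residual scatter of a two-parameter regression on a handful of timepoints, so the pivot is a t variable on n−2 degrees of freedom and the interval is too short at every planned series length.

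The same section judges fit by the overall regression p-value. In an ordinary linear regression that p-value allows for n−2 degrees of freedom, although the SAP does not say so. If so, one SE is treated as uncertain for the fit criterion and as known for the interval.

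At stake is the honesty of the 95% label on individual PRR48 values. Cohort 1 plans two participants per dose, so readers may lean on individual estimates.

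**Working it through.** **Inputs from the SAP**
- Level: 95%, two-sided (section 4).
- Multiplier: 1.96 whatever the series length (Equation 3).
- Parameters per fit: 2, so df = n−2 (Equation 1).
- Smallest n: 4 (11.1.2).
- Largest n in confinement: 15. SAP 10.4.1 gives one pre-dose sample ("On Day 8, blood will be collected pre-Pyronaridine tetraphosphate administration") and 14 post-dose times ("4, 8, 12, 16, 20, 24, 30, 36, 42, 48, 60, 72, 84 and 96 hours").

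**Step 1. The plan's own figure.** The two-sided 95% normal quantile is 1.95996, so Equation (3) yields 95% only with infinite df.

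**Step 2. Coverage with an estimated SE.** For a window fixed in advance and independent normal errors, coverage = 2 × F(1.96; n−2) − 1, where F is the t distribution function. PRR48 is a monotone function of the slope, so coverage is the same on the reported scale. The half-width on the log scale must grow by t(0.975, n−2) / 1.96.

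| n | df | t(0.975) | coverage with 1.96 | half-width ratio |
|---|---|---|---|---|
| 4 | 2 | 4.303 | 81.1% | 2.20 |
| 5 | 3 | 3.182 | 85.5% | 1.62 |
| 6 | 4 | 2.776 | 87.8% | 1.42 |
| 8 | 6 | 2.447 | 90.2% | 1.25 |
| 10 | 8 | 2.306 | 91.4% | 1.18 |
| 12 | 10 | 2.228 | 92.2% | 1.14 |
| 15 | 13 | 2.160 | 92.8% | 1.10 |

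If outpatient points extend the fit, coverage rises only slowly: 93.4% at n=20 and 94.0% at n=30.

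**Step 3. Size on the PRR48 scale.** Assume PRR48 = 100 (log10 = 2) and a fit that just meets p = 0.001. The log10 half-width is 2 × multiplier / |t|.
- n=8, |t| = 5.96. With 1.96: 2 × 1.96 / 5.96 = 0.658, giving 22 to 455. With t: 2 × 2.447 / 5.96 = 0.821, giving 15 to 663.
- n=4, |t| = 31.6. With 1.96: 2 × 1.96 / 31.6 = 0.124, a factor of 1.33 either way. With t: 2 × 4.303 / 31.6 = 0.272, a factor of 1.87.

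**Step 4. Effect of window selection.** The SAP's trimming steps were simulated on its 0–96 h sampling times. Slope, residual SD and lag are assumptions, not document figures. Coverage among fits with p<0.001:

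| Setting | 1.96 | t |
|---|---|---|
| 15 points, no lag, SD 0.3 | about 93% | about 95% |
| 15 points, 12 h lag, SD 0.3 | 82–84% | 85–88% |
| 15 points, no lag, SD 0.2 or 0.4, log10 PRR48 1–3 | 90–93% | 92–95% |
| 15 points, 12 h lag, SD 0.2 or 0.4, log10 PRR48 1–3 | 76–88% | 82–91% |
| 11 points, no lag, SD 0.2 or 0.4, log10 PRR48 2–3 | 81–90% | 87–94% |
| 11 points, 12 h lag, SD 0.2 or 0.4, log10 PRR48 2–3 | 62–76% | 71–83% |

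In every setting t did better than 1.96. With a lag it did not reach 95%.

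**The case against.** The strongest reply has four parts.

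*The fixed-window figures are not the procedure's coverage.* This stands. The SAP never uses a fixed window, so a reader should not take 81–93% as what the reported intervals will achieve. Step 4 shows that the result depends on lag and series length and can be lower.

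*Four-point fits are a corner case.* This also stands. At n=4, p<0.001 needs |t| above 31.6. In simulation, four-point windows made up at most 0.2% of passing fits at 15 points and at most 2.2% at 11. They were more frequent only with 8-point series, mostly where few fits passed. However, Equation (3) is not expressly restricted to fits that pass.

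*The t quantile does not repair the interval.* Partly right. It corrects the degrees-of-freedom error but not the selection effect, which is the larger cause of under-coverage in lagged profiles. That calls for a stated caveat and does not justify keeping 1.96.

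*Nothing depends on these limits.* Largely right. Dose-specific PRR48 and the between-dose tests (Equations 4–9) use the slopes and SEs directly, not the Equation (3) limits. The primary PK/PD analysis is a separate mixed-effects model. Section 4 calls the general approach descriptive. SAP 11.1.3 promises a listing of PRR48 and clearance half-life without naming individual CIs, although 11.1.2 says they are calculated.

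**Conclusion.** Equation (3) is wrong as written; the severity is minor. Before any allowance for window selection, its 95% interval covers 92.8% at n=15, 91.4% at n=10 and 90.2% at n=8, with 81.1% at n=4 as a rare extreme. These values are exact for a fixed window with independent normal errors. The selection results rest on assumed slopes, residual SDs and a 12 h lag, and the conclusion does not depend on them.

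Three stronger readings are tempting, and the documents do not support them:
- That a t multiplier would make these true 95% intervals. It does so only for a window fixed in advance, which the SAP does not use.
- That the error reaches point estimates, dose-specific PRR48, between-dose tests or the primary model. None of them uses the Equation (3) limits.
- That the over-precision demonstrably falls on fast clearers or on participants with low starting parasitaemia. This is plausible, because the series stops at the first timepoint with all replicates non-detectable, but the documents give no series lengths to show it.

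**What to change.** In SAP 11.1.2, Equation (3), replace 1.96 by t(0.975, n_i − 2), where n_i is the number of timepoints in participant i's selected regression. Report n_i beside each participant's PRR48. Add a sentence that the interval is conditional on the selected window and may cover less than 95% because that window is chosen by minimum p-value.

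The cost is one symbol in the SAP, one line of R and one listing column; no new data are needed. The downside is wider individual intervals: about 10% wider at n=15 and 25% at n=8 on the log scale, and 2.2 times as wide in the rare four-point fit.

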9.4.3 ANALYSIS OF THE SECONDARY ENDPOINTS

This study has three secondary endpoints.

Safety parameters:

The safety and tolerability of pyronaridine will be assessed by clinical review of the following parameters:

- AEs (including SAEs and AESIs)
- Vital signs
- 12-lead ECG
- Haematology, Biochemistry, urinalysis
- Physical examination

The analysis of this endpoint is discussed in Section 9.4.4 below.

Parasite clearance kinetics:

The parasite clearance kinetics following dosing with of pyronaridine will be determined by calculating the parasite reduction ratio over a 48 hour period (PRR₄₈) and corresponding parasite clearance half-life (PCt_{1/2}); the incidence of parasite regrowth (n and % per dose group) will be recorded.

The PRR₄₈ will be estimated using the slope of the optimal fit of the log-linear relationship of the parasitaemia decay. The optimal fit will be derived using summarised replicate parasitaemia data, which have been cleaned by dealing with potential outliers, values below the limit of detection and non-detectable values (ND). The optimal fit of the log-linear parasitaemia-by-time relationship is determined by using left and right censoring to systematically remove the potential lag phase and tail phase of the parasitaemia decay. The decay rate, estimated by the slope coefficient from the log-linear decay regression, will be calculated for each participant. The overall dose-specific PRR₄₈ will be estimated with its 95% CI by calculating the weighted average slope estimate and corresponding standard error (SE) using an inverse-variance method. Only participants who have optimal regression models with appropriate fit contribute toward the dose-specific PRR₄₈. Details will be presented in the SAP.

The parasite clearance half-life (Pt ½) will be derived from the optimal decay rate. PCt_{1/2} is a transformation of PRR₄₈ into a per hour clearance rate. Details regarding the calculation of this parameter will be presented in the SAP.

PK parameters:

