The weight for the j^{th} dose is denoted by $w_{j.} = \sum_{i=1}^{s_j} w_{ij}$ for participant i with appropriate overall fit in dose j . The $\bar{\beta}_{j.}$ is the weighted average slope for dose j as defined in Equation (9), and $\bar{\beta}_{..}$ is the weighted grand mean given by:

$$\bar{\beta}_{..} = \frac{\sum_{j=1}^J w_{j.} \bar{\beta}_{j.}}{\sum_{j=1}^J w_{j.}} \quad (9)$$

Post-hoc pair-wise comparisons can be calculated using the test statistic $Z_G = \frac{G}{\sqrt{v_G}}$, where G is the contrast ($G = c_1 \bar{\beta}_1 + \dots + c_J \bar{\beta}_J$) and v_G is the variance of the contrast ($v_G = \frac{c_1^2}{w_{1.}} + \dots + \frac{c_J^2}{w_{J.}}$). The p-value of the L pair-wise comparisons can be calculated using the Scheffe method, by comparing Z_G^2 to a chi-squared distribution with $L - 1$ degrees of freedom.

Parasite Regrowth

Incidence of parasite regrowth will be reported as the number and percentage of participants in each dose group, with regrowth defined as ≥ 5000 parasites/mL and a two-fold parasitaemia increase within 48 hours after initial reduction in parasitaemia.

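### The dose-specific PRR48 confidence intervals and dose-comparison tests leave out between-participant variation, so the CIs are too narrow and the tests over-reject whenever clearance slopes differ between people

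*SAP*

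**What the plan says.** SAP 11.1.2 fits a log-linear regression to each participant's parasitaemia. It then combines the slopes of participants whose fit has p < 0.001.

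- **Pooling.** The dose average is "estimated by using the inverse variance method to calculate the weighted average linear regression slope", "where the weight is the inverse of the squared standard error". The pooled SE is the square root of 1/Σw (the text after Equation 4), and Equation 6 forms the CI with 1.96 times that SE.
- **Dose comparison.** To look for dose differences, "an omnibus test for between group differences is used". The statistic Q_B (Equation 8) sums the weighted squared deviations of the dose means and is referred to chi-square with J − 1 df, J being the number of doses.
- **Pairwise contrasts.** "The p-value of the L pair-wise comparisons can be calculated using the Scheffe method". The contrast variance again uses the summed weights, and the reference is chi-square with L − 1 df.
- **Protocol.** Section 9.4.3 plans the same pooling, "calculating the weighted average slope estimate and corresponding standard error (SE) using an inverse-variance method", but no test between doses.
- **Nominal levels.** SAP 4: "CIs will be two-sided and will use 95% confidence levels" and "Any analyses requiring significance testing will use a two-sided test at the 5% significance level".

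**The concern.** This is a fixed-effect pool. The only error it recognises is the scatter of points about each participant's own line. Participants are randomised to dose, so the dose means also differ because different people are in each group, and neither the CI nor Q_B allows for that. The SAP does not hold that people respond alike: its PD model (10.6.3) puts inter-individual variability on every parameter except the Hill coefficient. None of that variability reaches the PRR48 interval or tests.

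PRR48 is a named secondary endpoint, and this is the only dose-difference test the SAP specifies. With two participants per dose in Cohort 1, an ordinary difference between people could be read as a dose effect.

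**Working it through.** **Inputs from the documents.** Two-sided 95% CI and 5% tests (SAP 4); the weights, pooled SE, Q_B and contrasts above (SAP 11.1.2); three listed doses (SAP 3.1, 4.2.4); two participants per dose in Cohort 1 and at most 18 overall (SAP 3.1); pre-dose plus 14 qPCR samples to 96 h (SAP 10.4.1).

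**Not given.** The between-participant SD of the slope (τ), the within-participant slope SE, the qPCR residual SD and the expected PRR48. Results are therefore stated as a function of r = τ/SE. Since log10 PRR48 is −48 times the slope, coverage is the same on either scale.

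**Formulas, for equal and known SEs and n participants per dose.** The reported variance of a dose mean is SE²/n and the true variance is (SE² + τ²)/n. Their ratio is 1 + r², which does not involve n, so adding participants does not correct the error.

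- Coverage = 2Φ(1.96/√(1 + r²)) − 1.
- Omnibus rejection with equal true doses = P(χ²(J−1) > c/(1 + r²)), where c is the 5% critical value. At J = 3, c = 5.991 and this simplifies to 0.05^(1/(1 + r²)).

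**Results (J = 3).** The row r = 0 reproduces the plan's nominal levels.

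| r | √(1 + r²) | CI coverage | Omnibus false positives |
|---|---|---|---|
| 0 | 1.00 | 95% | 5% |
| 0.5 | 1.12 | 92% | 9% |
| 1 | 1.41 | 83% | 22% |
| 2 | 2.24 | 62% | 55% |
| 3 | 3.16 | 46% | 74% |

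At r = 2 the omnibus rate is 38% with J = 2 and 67% with J = 4. A single Scheffé contrast at J = 3 rejects 1.4% of the time at r = 0, 8% at r = 1 and 44% at r = 3.

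**What the SAP's own filter implies.** A fit enters the pool only if p < 0.001, so SE/|slope| cannot exceed 1/t(0.9995, n_points − 2). That is 0.237 with 15 points and 0.168 with 8. If the slope CV were 20% (an assumption) and every SE sat at that limit, r would be 0.2/0.237 = 0.84 or 0.2/0.168 = 1.19. Coverage would then be about 87% or 79%, and omnibus error about 17% or 29%. This is the favourable end for that CV, treating estimated SEs as true ones.

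**Simulation of the full algorithm** (sampling times, stop at first non-detect, minimum-p window search, p < 0.001 filter, Equations 4 to 8, J = 3). All variability inputs are assumptions.

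| Slope CV | log10 PRR48 | Residual SD (log10) | Coverage | Omnibus |
|---|---|---|---|---|
| 20% | 1.5–2.5 | 0.2–0.5 | 18–69% | 39–90% |
| 10% | 2 | 0.2–0.3 | 55–73% | 37–55% |
| 0 | assumed range | assumed range | 89–93% | 6–12% |

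The last row is the part due to estimated SEs, window selection and truncation alone. In a simplified run without the window search (20% CV, log10 PRR48 = 2, residual SD 0.22), the mean reported SE of log10 PRR48 was 0.14 against a true 0.34 at n = 2 (ratio 2.4), and 0.078 against 0.205 at n = 6 (ratio 2.6).

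**Check of the remedy.** Unweighted slopes with a pooled between-participant SD and t/F references gave 95% coverage and 5% omnibus error at r = 0, 1, 2.2 and 3 and n = 2, 4 and 6. In a separate run of the full algorithm (log10 PRR48 = 2, residual SD 0.22), ANOVA on slopes covered about 93–96%. A random-effects τ² with z and chi-square references is not enough: at r = 2.2 it gave 87% and 18% at n = 2, and 93% and 8% at n = 6.

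**Two smaller items.**

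- Individual CIs (Equation 3) use 1.96 whatever the number of points. With four points (2 df) that covers 81%.
- Scheffé needs J − 1 df, not L − 1 with L the number of pairwise comparisons. The two agree at J = 3 (L = 3). At J = 2, L − 1 = 0 and no p-value exists. At J = 4, L − 1 = 5 gives a critical value of 11.07 instead of 7.81, which is conservative.

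**The case against.** The fixed-effect interval can be defended as describing the precision-weighted mean of these particular participants. That does not rescue a quantity labelled as dose-specific and compared across randomised groups, where the relevant error includes who was allocated to which dose.

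The case for limited consequences is stronger, and most of it stands. Protocol 9.1 pre-specifies no hypothesis for the primary objective, and SAP 4 calls the approach to all endpoints descriptive. The protocol plans a PRR48 interval but no dose test, and the SAP makes the pairwise tests optional. Dose choice and stopping rest on SDRT review (Protocol 4.1, 9.2, 10.1.8), and no stated decision uses Q_B. The PK/PD analysis models inter-individual variability and derives its own PRR48 by dose (SAP 10.7). Individual PRR48 values and fits will be reported (SAP 11.1.3), so a reader could see the heterogeneity. That ordinary differences will be reported as dose effects is therefore a risk, not a certainty.

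The smaller items are also limited. A four-point fit must reach |t| > 31.6 to pass p < 0.001. In one full-algorithm run the chosen window had a median of 15 points, where t is 2.16 (13 df), and no four-point fits occurred; faster clearance would leave fewer points. The Scheffé slip has no effect with the three listed doses.

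**Conclusion.** The omission is certain, because it is in the formulas and nothing elsewhere in either document supplies the missing term. Its size is conditional. For r of 1 to 3 with three doses and equal known SEs, coverage falls to about 83–46% and omnibus error rises to about 22–74%.

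Two stronger readings are tempting, and the documents do not support them:

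- **A single figure**, such as coverage of 55–60% with 60% false positives. This needs r of about 2.2 and J = 3, and it comes from a simplified calculation. The full algorithm under similar assumptions gave about 35% and 85%.
- **That the SAP supplies the slope variation.** The SD of 0.2 in SAP 10.6.3 is a fixed working value for the SysFit PD parameters and acts as a quadratic prior (10.6.1). Monolix then estimates those SDs. It is not an expected SD of the log-linear clearance slope. It makes material under-coverage plausible but does not set its size.

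Nor does the problem reach the primary PK/PD model. It is confined to the secondary PRR48 intervals and the dose-difference tests. It should be fixed; the df corrections are minor.

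**What to change.** In SAP 11.1.2:

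1. Take each participant's slope as the unit of analysis. Estimate dose means with a between-participant variance pooled across doses, by one-way ANOVA on slopes or by a mixed model with random participant slopes.
2. Use t with N − J df for the dose CIs, N being the participants with an acceptable fit, and an F test in place of Q_B. Do not rely on z or chi-square references at these sample sizes.
3. Use t with n − 2 df for individual CIs, n being the points in the chosen window.
4. Use J − 1 df for any Scheffé comparison.
5. Align Protocol 9.4.3, or declare the change in SAP 13.

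The cost is SAP wording, a few lines of R and wider intervals. If slopes truly did not vary, the widening from the t multiplier would be 2.13/1.96 = 1.09 at N = 18 and J = 3 (15 df), and 3.18/1.96 = 1.62 at N = 6 (3 df). If they do vary, the typical further widening is the √(1 + r²) factor in the table, which is the uncertainty the current formula leaves out.
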